6.2.9 Study Day 1 (day of first study substance administration) – Remote

Study staff will confirm the first dose taken by the participant by telephone. Participants who refuse the first dose after 2 days will be discontinued from the study.

Study staff will also confirm by telephone the completion of first nasal swab home kit to be mailed out within 24 hours. The nasal swab home kit can be completed within days 1 to 3 to accommodate shipping limitations.

The participant will utilize an application (app) available to self-report symptoms once daily as Patient-reported outcomes (PRO). The application clarifies to the study participant the information they are providing is not a substitute for standard COVID-19 care with their health care provider. The participant's completion of the self-report or PRO will be reviewed. If the participant does not complete their self-report, study staff will initiate contact to facilitate the completion of the daily self-report PRO. If the self-report or PRO discloses onset or worsening of the symptom of shortness of breath or worsening of other symptoms the participant will be instructed to call 911, telephone their health care provider or go to the health care provider urgent or emergency care facility.

Study staff will obtain and review the participant's EHR for pertinent information for the primary, secondary and exploratory endpoints.

6.2.10 Study Day 3 – Remote

The participant will continue to self-administrate the study agent twice a day daily. They will have an application available to self-report taking the daily doses. The participant will also self-report symptoms to the same application once daily. The application clarifies to the study participant the information they are providing is not a substitute for standard COVID-19 care with their health care provider. The participant's completion of the self-report or PRO will be reviewed. If the participant does not complete their self-report, study staff will initiate contact to facilitate the completion of the daily self-report PRO. If the self-report or PRO discloses onset or worsening of the symptom of shortness of breath or worsening of other symptoms the participant will be instructed to call 911, telephone their health care provider or go to the health care provider urgent or emergency care facility.

Study staff will obtain and review the participant's EHR for pertinent information for the primary, secondary and exploratory endpoints.

If the participant has had a resolution of listed symptoms for 3 days, study staff will confirm by telephone and change contact schedule to once weekly.

6.2.11 Study Day 7 – Remote

Study staff will also confirm by telephone the completion of the second nasal swab home kit to be mailed out within 24 hours. The nasal swab home kit can be completed within days 7 to 9 to accommodate shipping limitations.

The participant will continue to self-administrate the study agent twice a day daily. They will have an application available to self-report taking the daily doses. The participant will also self-report symptoms to the same application once daily. The application clarifies to the study participant the information they are

providing is not a substitute for standard COVID-19 care with their health care provider. The participant's completion of the self-report or PRO will be reviewed. If the participant does not complete their self-report, study staff will initiate contact to facilitate the completion of the daily self-report PRO. If the self-report or PRO discloses onset or worsening of the symptom of shortness of breath or worsening of other symptoms the participant will be instructed to call 911, telephone their health care provider or go to the health care provider urgent or emergency care facility.

Study staff will obtain and review the participant's EHR for pertinent information for the primary, secondary and exploratory endpoints.

If the participant has had a resolution of listed symptoms for 3 days, study staff will confirm by telephone and change contact schedule to once weekly.

6.2.12 Study Day 14 – Remote

Study staff will confirm by telephone the completion of the final nasal swab home kit to be mailed out within 24 hours. The nasal swab home kit can be completed within days 14 to 16 to accommodate shipping limitations.

The participant will self-administrate the last two doses of the study agent and self-report taking daily dose for last time. Study staff will contact by telephone to verbally confirm the number of doses taken to reconcile any differences with the self-report.

The participant will continue to self-report symptoms to the application once daily. The application clarifies to the study participant the information they are providing is not a substitute for standard COVID-19 care with their health care provider. The participant's completion of the self-report or PRO will be reviewed. If the participant does not complete their self-report, study staff will initiate contact to facilitate the completion of the daily self-report PRO. If the self-report or PRO discloses onset or worsening of the symptom of shortness of breath or worsening of other symptoms the participant will be instructed to call 911, telephone their health care provider or go to the health care provider urgent or emergency care facility.

Study staff will obtain and review the participant's EHR for pertinent information for the primary, secondary and exploratory endpoints.

If the participant has had a resolution of listed symptoms for 3 days, study staff will confirm by telephone and change contact schedule to once weekly.

6.2.13 Study Day 21 – Remote

Study staff will contact by telephone to verbally reconcile any differences with the self-report.

The participant will continue to self-report symptoms to the application once daily. The application clarifies to the study participant the information they are providing is not a substitute for standard COVID-19 care with their health care provider. The participant's completion of the self-report or PRO will be reviewed. If the participant does not complete their self-report, study staff will initiate contact to facilitate the completion of the daily self-report PRO. If the self-report or PRO discloses onset or worsening of the symptom of shortness of breath or worsening of other symptoms the participant will be instructed to call 911, telephone their health care provider or go to the health care provider urgent or emergency care facility.

Study staff will obtain and review the participant's EHR for pertinent information for the primary, secondary and exploratory endpoints.

6.2.14 Study Day 28 – Remote

The participant will self-report symptoms to the application for the last time. The application clarifies to the study participant the information they are providing is not a substitute for standard COVID-19 care with their health care provider. The participant's completion of the self-report or PRO will be reviewed. If the participant does not complete their self-report, study staff will initiate contact to facilitate the completion of

the daily self-report PRO. If the self-report or PRO discloses onset or worsening of the symptom of shortness of breath or worsening of other symptoms the participant will be instructed to call 911, telephone their health care provider or go to the health care provider urgent or emergency care facility.

Study staff will obtain and review the participant's EHR for pertinent information for the primary, secondary and exploratory endpoints.

6.2.15 Study Day 42 – Remote

Study staff will contact by telephone to gather pertinent information for the primary, secondary and exploratory endpoints. If the self-report or PRO discloses onset or worsening of the symptom of shortness of breath or worsening of other symptoms the participant will be instructed to call 911, telephone their health care provider or go to the health care provider urgent or emergency care facility.

Study staff will obtain and review the participant's EHR for pertinent information for the primary, secondary and exploratory endpoints.

6.2.16 Study Week 12 – Remote

Study staff will contact by telephone to gather pertinent information for the primary, secondary and exploratory endpoints. If the self-report or PRO discloses onset or worsening of the symptom of shortness of breath or worsening of other symptoms the participant will be instructed to call 911, telephone their health care provider or go to the health care provider urgent or emergency care facility.

Study staff will obtain and review the participant's EHR for pertinent information for the primary, secondary and exploratory endpoints.

6.2.17 Discontinuation Evaluations

Evaluations for Participants Who Do Not Start Study Treatment

Participants who are randomized but do not take the first (directly observed/confirmed) dose of study treatment do not need to be followed. An off study eCRF should be completed recording this and any evaluations completed for these participants should also be recorded on the Day 0 eCRFs.

Premature Treatment Discontinuation Evaluations

Participants who discontinue study treatment early should remain on study and all evaluations should be performed as outlined in the SOE.

Premature Study Discontinuation Evaluations

Participants who discontinue study participation should undergo premature study discontinuation evaluations as outlined in the SOE within 14 days of study discontinuation. If study discontinuation occurs on or prior to Day 13, all procedures should be performed as described in the SOE for premature study discontinuation evaluations. If study discontinuation occurs after Day 13, all evaluations EXCEPT treatment adherence should be performed.

For participants who prematurely discontinue from the study for reasons other than withdrawal of consent, sites will attempt to obtain information regarding vital status and endpoints per the SOE (see [section 6.1](#)).

6.2.18 COVID-19 Symptom Screen

Participants will be asked about their first symptoms related to COVID-19 and their current symptoms, to document eligibility. This will include when and what symptoms the participant noticed having. This data will be collected via the Study App.

6.2.19 Medical History

The medical history must include all signs and symptoms regardless of grade and all diagnoses within the past 14 days. This data will be collected via the Study App.

6.2.20 Medication History

A medication history must be present, including drug name, dosage, and indication, for the past 3 months. The participants will be able to type it out into a word box in the Study App.

6.2.21 Clinical Assessments

Some events require clinical evaluations by the patient/participants health care providers. Copies of these encounters by the health care providers will be obtained by the study team for review, documentation and coding.

Refer to [section 7.2](#) for AE collection requirements.

6.2.22 Concomitant Medications

At entry and post-entry, we will record new and discontinued concomitant medications.

6.2.23 Study Treatment (Intervention) Modifications

Record any modification to treatment, treatment interruption, and permanent discontinuation of treatment, and the reason for the modification, interruption, or discontinuation.

6.2.24 Secondary Contact

Sites will capture secondary contact information for two individuals that the site can contact if the participant cannot be reached (e.g., spouse, friend, neighbor, etc.).

7 ADVERSE EVENTS AND STUDY MONITORING

7.1 *Definition of Adverse Events*

An AE is any unfavorable and unintended sign, symptom, or diagnosis that occurs in a study participant during the conduct of the study REGARDLESS of the attribution (i.e., relationship of event to medical treatment/study product/device or procedure/intervention). This includes any occurrence that is new in onset or aggravated in severity or frequency from the baseline condition.

Information sources include study assessments including daily and weekly PRO of telephone calls; health information obtained from the patients' health care providers and health system encounters including outpatient visits, urgent care, emergency room or inpatient visits.

Review by the study coordinator and medical monitor will be performed and those deemed a clinically significant worsening from baseline will be documented as an AE.

A clinically-significant finding could include: worsening from baseline (eg, by at least 1 grade); concomitant signs or symptoms related to the abnormal study assessment; further diagnostic testing or medical/surgical intervention required; if study drug is withheld, or discontinuation from study drug. Determination of clinical significance must be made by the medical monitor.

Events that do not meet the definition of an AE or SAE include: planned hospital admissions or surgical procedures for a condition that existed before the subject signed the informed consent are not to be considered AEs unless the condition deteriorates in an unexpected manner during the study (eg, surgery had to be performed earlier than planned); anticipated day-to-day fluctuations of pre-existing disease(s), condition(s), and signs or symptoms present or detected prior to the start of the study that are not more severe than expected for the subject's condition; and worsening of the COVID-19 including hospitalization, or death due to COVID-19.

7.2 *Adverse Event Collection Requirements for This Protocol*

Post-entry, all AEs must be recorded on the eCRFs **within 72 hours** if any of the following criteria have been met:

- All Grade ≥ 2 AEs
- All AEs that led to a change in study treatment/intervention regardless of grade
- All AEs meeting SAE definition

Serious Adverse Events (SAEs)

An SAE is defined as any untoward medical occurrence that:

- Results in death
- Is life-threatening illness
- Requires inpatient hospitalization or prolongation of existing hospitalization
- Results in persistent or significant disability/incapacity
- Is a congenital anomaly/birth defect.
- Is an important medical event that may not be immediately life-threatening or result in death or hospitalization but may jeopardize the patient or may require intervention to prevent one of the other outcomes listed in the definition above).

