Summary: Today, in China, mild and moderate cases are mainly treated with comprehensive TCM. The rate of mild or moderate cases progressing to severe was significantly reduced. Before the widespread usage of TCM, nationwide China saw a progression of disease of about 10% of their mild/moderate cases while after TCM utilization, the percentage dropped to 2-5% depending on the hospital. Overall, they saw an improvement in clinical symptoms. [see personal correspondence with [name] [name] dated March 31, 2020]. Due to the challenges of the rapidly evolving outbreak, these are clinical observations and not evidence from a controlled study.

Preclinical Studies of XFBD

Tianjin University of Traditional Chinese Medicine conducted an acute toxicity study for XFBD in mice at the concentrations of 91.39 g/kg, 114.24 g/kg, and 142.8 g/kg by single gavage followed by a 14-day observation. The data showed that mice given 142.8 g/kg appeared to be in prone positions with movement reduction, which resolved within 4 hours. The female mice in 142.8 g/kg group had soft or loose stools, but the mice recovered on the 4th day. No significant differences were found in the body weight between mice in the administration group and control group when measured on the 1st, 3rd, 7th, and 14th day after administration. No deaths were observed in the 14 days. After gross anatomical observation, there were no apparent abnormalities found in mice from either group. Therefore, we conclude that the maximum tolerated dose of XFBD given by single gavage in mice should be more than 142.8 g /kg (equivalent to 84 times of the clinical dosage). [personal correspondence with [name], dated Apr 28, 2020]

Long term toxicity studies are ongoing and will be updated as data becomes available.

While all medicinals in the XFBD are widely used and within the appropriate dosing range, formal toxicity studies have not been conducted. Symptom comparisons and toxicities will be one part of both the pilot and the complete trial.

XFBD Availability

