8.3.2 Cardiovascular Effects

Rapid heart rate, decreased heart rate, palpitations, increased blood pressure, decreased blood pressure, dizziness, fainting, cyanosis are listed as potential side effects of the components of XFBD.

Table 8.3.2 – Selected Cardiovascular Adverse Event Grading (CTCAE)

Grade	1	2	3	4	5
Chest pain – cardiac	Mild pain	Moderate pain; pain on exertion; limiting instrumental ADL; hemodynamically stable	Pain at rest; limiting self care ADL; cardiac catheterization; new onset cardiac chest pain; unstable angina		
Cyanosis		Present			
Dizziness	Mild unsteadiness or sensation of movement	Moderate unsteadiness or sensation of movement; limiting instrumental ADL	Severe unsteadiness or sensation of movement; limiting self care ADL		
Hypertension	Systolic BP 120 - 139 mm Hg or diastolic BP 80 – 89 mm Hg;	Systolic BP 140 – 159 mm Hg or diastolic BP 90-99 mm Hg if previously WNL; change in baseline medical intervention indicated; recurrent or persistent (≥ 24 hrs); symptomatic increase by	Systolic BP \geq 160 mm Hg or diastolic BP \geq 100 mm Hg; medical intervention indicated; more than one drug or more intensive therapy than previously used indicated;	Life threatening consequences (e.g., malignant hypertension, transient or permanent neurologic deficit, hypertensive crisis); urgent intervention indicated	Death

		>20 mm Hg (diastolic) or to >140/90 mm Hg; monotherapy indicated initiated			
Hypotension	Asymptomatic, intervention not indicated	Non-urgent medical intervention indicated	Medical intervention indicated; hospitalization indicated	Life-threatening consequences and urgent intervention indicated	Death
Palpitations	Mild symptoms; intervention not indicated	Intervention indicated			
Syncope				Fainting, orthostatic collapse	

In the event of grade 1 or greater cardiovascular symptoms, the study staff must refer the participant to their primary health care providers. For grade 2 or greater events participants must be referred to their health care provider for evaluation and study agent is discontinued.

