8.3.3 Nervous and Psychiatric Events

Headache, psychosis, insomnia, heatstroke, nervousness, anxiety, strokes, seizures, coma; are listed as potential side effects of the components of XFBD.

Table 8.3.3 – Selected Nervous System and Psychiatric Adverse Event Grading (CTCAE)

Grade	1	2	3	4	5
Anxiety	Mild symptoms; intervention not indicated	Moderate symptoms; limiting instrumental ADL	Severe symptoms; limiting self-care ADL; hospitalization indicated	Life-threatening consequences; urgent intervention indicated	
Depressed levels of consciousness	Decreased level of alertness	Sedation; slow response to stimuli; limiting instrumental ADL	Difficult to arouse	Life-threatening consequences; coma; urgent intervention indicated	
Headache	Mild pain	Moderate pain; limiting instrumental ADL	Severe pain; limiting self-care ADL		
Insomnia	Mild difficulty falling asleep, staying asleep or waking up early	Moderate difficulty falling asleep, staying asleep or waking up early	Severe difficulty falling asleep, staying asleep or waking up early		
Psychosis	Mild psychotic symptoms	Moderate psychotic symptoms (disorganized speech;	Severe psychotic symptoms (paranoid, extreme	Life-threatening consequences; threats of harm to self or others;	Death

		impaired reality testing)	disorganization) hospitalization not indicated; new onset	hospitalization indicated	
Stroke	Incidental radiographic findings only	Mild to moderate neurologic deficit; limiting instrumental ADL	Severe neurologic deficit; limiting care ADL; hospitalization	Life-threatening consequences; coma; urgent intervention indicated	Death
Seizure	Brief partial seizure and no loss of consciousness	Brief generalized seizure	New onset seizures (partial or generalized); multiple seizures despite medical intervention	Life-threatening consequences; prolonged repetitive seizures	Death

Grade 1 Anxiety and insomnia do not require treatment discontinuation. For grade 2 anxiety or insomnia the study agent is discontinued. For all other grade 1 or greater events in table 8.3.3 participants are instructed to discontinue study medication or placebo and must be referred to their health care provider for management.

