10.2.1 Primary Outcome Measure

- 10.2.1.1 To document the feasibility of recruitment in the community setting by assessment of the number of positive cases identified per week.
- 10.2.1.2 To document the proportion of patients who agree to participate as measured by enrollment and randomization.
- 10.2.1.3 To document the treatment emergent side effects and safety profile of the XFBD and placebo.
- 10.2.1.4 To document the rate of hospitalization or death within 42 days of enrollment in the XFBD and placebo treated groups.

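### Section 7.2 does not require mild adverse events to be recorded for 12 of the 23 terms with a grade 1 definition, although the primary side-effect outcome has no grade limit and no source is named for grade 1 events

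*Combined protocol and SAP*

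**What the plan says.** Section 7.2, whose heading presents it as the AE collection requirements of the protocol, asks for eCRF entry within 72 hours when an event falls in one of three classes: "All Grade ≥ 2 AEs"; "All AEs that led to a change in study treatment/intervention regardless of grade"; and "All AEs meeting SAE definition". No other section requires entry of the AEs that fall outside these classes.

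The third primary outcome (10.2.1.3) is "To document the treatment emergent side effects and safety profile of the XFBD and placebo". It carries no grade limit. Grade 3 and 4 events have their own secondary outcome (10.2.2.6). Section 10.6.1 plans logistic or negative binomial regression for this primary outcome, but does not say which data it is built from.

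Three other places bear on mild events:

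- Section 7.1 says that, after review by the study coordinator and medical monitor, "those deemed a clinically significant worsening from baseline will be documented as an AE". A worsening of at least one grade is given as an example of what could count, and the medical monitor decides.
- Section 8.3 says that the daily and weekly app reports include potential AEs. Section 10.6.2 has each symptom rated 0–4 and sums the ratings into a severity score.
- Sections 8.3.1–8.3.4 set stopping rules by term. For cardiovascular terms: "For grade 2 or greater events participants must be referred to their health care provider for evaluation and study agent is discontinued". For nervous and psychiatric terms other than anxiety and insomnia: "For all other grade 1 or greater events in table 8.3.3 participants are instructed to discontinue study medication or placebo".

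The subsection on preclinical studies states that formal toxicity studies of XFBD have not been done and adds: "Symptom comparisons and toxicities will be one part of both the pilot and the complete trial".

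**The concern.** A primary outcome on side effects at all grades needs a record of side effects at all grades. Section 7.2 sets a floor at grade 2. Below it, a non-serious event must be entered only if treatment was changed. For a protocol-driven stop, that depends on the rule in section 8.3 for that term.

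The floor matters most for stimulant effects. Table 8.2 lists palpitations, raised blood pressure, dizziness, insomnia and anxiety for Ephedrae Herba. In Table 8.3.2 palpitations reach grade 2 only when intervention is indicated, so palpitations that need none can leave no required AE entry. The same is true of grade 1 cardiovascular symptoms that staff must refer to the participant's own provider.

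This pilot has remote visits, no data monitoring committee (10.5) and no formal toxicity studies behind it, so reported symptoms are a main source of safety information. An AE table with few or no mild stimulant events in either arm could be taken as good tolerability when the larger trial is planned.

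**Working it through.** The plan gives no figure to reproduce here. The check is a count of terms, followed by an illustration.

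**Step 1. Count the terms.** Take every term in Tables 8.3.1–8.3.4 with a grade 1 definition. Cyanosis and syncope (8.3.2) and hepatic failure (8.3.4) have none. Then apply the stopping rule in the subsection of each table.

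| Table | With a grade 1 | Grade 1 stops treatment, so 7.2 applies | Grade 1 meets no 7.2 criterion |
|---|---|---|---|
| 8.3.1 | 4 | 0 | 4: abdominal pain, nausea, diarrhea, vomiting |
| 8.3.2 | 5 | 0 | 5: chest pain, dizziness, hypertension, hypotension, palpitations |
| 8.3.3 | 7 | 5: depressed consciousness, headache, psychosis, stroke, seizure | 2: anxiety, insomnia |
| 8.3.4 | 7 | 6: urinary frequency, dehydration, hypoglycemia, low white cells, testosterone deficiency, hematuria | 1: fatigue |
| Total | 23 | 11 | 12 |

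So 12/23 = 52% of the terms meet no criterion at grade 1, unless the event is serious or treatment changes for another reason. The graded stimulant-type terms (palpitations, hypertension, dizziness, anxiety, insomnia) are all among the 12. Of the 11 on the other side, five of the six from Table 8.3.4 (all but urinary frequency) are seen only through medical records after a health care encounter.

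**Step 2. Compare with the general rule.** Section 8.3 stops study agent only for events above grade 1. Sections 8.3.3 and 8.3.4 stop it at grade 1 for the 11 terms. These passages contradict each other.

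- If the term-specific rules govern, 11 of 23 terms are recorded from grade 1 and 12 from grade 2.
- If the general rule governs, no grade 1 event triggers a protocol stop. None of the 23 then enters by that route, and the difference between terms disappears.

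**Step 3. Illustrate the loss.** Inputs: 30 per arm (section 3). Assumed, not from the documents: a stimulant symptom in 20% on XFBD and 5% on placebo; a share g of cases at grade 1, equal in both arms; the term does not stop treatment at grade 1; nothing is added through 7.1.

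- Recorded rate = p(1 − g)
- Expected recorded participants = 30 × p(1 − g)
- Chance of no record on XFBD = (1 − p(1 − g))^30

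| Capture | XFBD, expected | Placebo, expected | Risk difference | Chance of no record on XFBD |
|---|---|---|---|---|
| All grades | 6.0 | 1.5 | 0.15 | 0.80^30 = 0.1% |
| 7.2 floor, g = 0.5 | 3.0 | 0.75 | 0.075 | 0.90^30 = 4% |
| 7.2 floor, g = 0.7 | 1.8 | 0.45 | 0.045 | 0.94^30 = 16% |
| 7.2 floor, g = 0.9 | 0.6 | 0.15 | 0.015 | 0.98^30 = 55% |

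With g equal in both arms the risk ratio is unchanged: 0.20(1 − g) / 0.05(1 − g) = 4. What shrinks is the absolute difference and the number of events available to describe it.

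**The case against.** The strongest reply is that mild symptoms are collected. The app asks about symptoms every day; its visible screens in Appendix VI include anxiety, abdominal pain, chest pain and chest tightness, and 7.1 names these reports as a source of AE information. A reader might infer from 7.2 that the trial cannot see mild stimulant effects. The documents do not support that. Nor do they show that palpitations or insomnia are missing from the app, because only part of the list is visible. What remains is narrower: the only stated analysis of the symptom ratings is a summed score, daily, weekly and as an area under the curve, which reports no individual term. No mapping from the 0–4 scale to CTCAE grade is given, and 10.6.1 does not name the app as a source.

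Second, 7.1 has no grade floor, and 7.3 assesses the relationship to study drug for all AEs. Both points are correct. But 7.1 leaves the decision to the medical monitor and names no eCRF entry, and 7.3 says how an AE is classified, not which AEs must be entered.

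Third, grade 1 cardiovascular symptoms must be referred, and encounter records are obtained for review and coding (6.2.21, 8.3). This helps only if an encounter takes place, and 7.2 still does not require entry at grade 1.

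Fourth, 7.2 could be read as a 72-hour timing rule only. Its heading speaks against this, and on that reading no section says when or whether the remaining AEs are entered.

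Fifth, a reader might infer that the AE table must be distorted between terms. That follows only if 8.3.3 and 8.3.4 override 8.3, which the documents leave open. Nor does the floor favor one arm by design, since both blinded arms are treated alike.

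**Conclusion.** The point holds as a mismatch between a required record and a primary outcome. At grade 1, 12 of 23 listed terms (52%) meet no recording criterion in 7.2, and the other 11 qualify only under stopping rules that conflict with 8.3. Mild effects can therefore be absent from the AE record in both arms, which would shrink the absolute difference that the pilot is meant to describe.

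The 52% counts terms. The share of events that would be lost cannot be derived from the documents, so it should not be read as saying that most mild events go unrecorded. The figures in the illustration rest wholly on assumed rates and grade shares. The conclusion also assumes that the primary outcome would be built from the eCRF AE record, which 10.6.1 neither confirms nor excludes.

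This should be corrected. It does not affect the hospitalization or recruitment outcomes, and confidence in the recording gap itself is high.

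**What to change.** - **7.2:** require treatment-emergent AEs of every grade on the eCRF, at least for the terms in Tables 8.3.1–8.3.4. Keep the 72-hour deadline only for the three classes now listed.
- **Baseline:** section 6.2.19 already collects signs and symptoms at baseline whatever their grade. Use these as the reference for new or worse, with the grade written down.
- **7.1:** align it with 7.2, so that a one-grade worsening is not left to discretion in one section and below the floor in the next.
- **10.6.1 and 10.2.1.3:** name the data source, and report by arm, term and maximum grade with grade 1 included. Draw on the item-level app reports for mild symptoms, with a stated mapping from the 0–4 rating to CTCAE grade.
- **8.3 against 8.3.3 and 8.3.4:** reconcile the stopping rules. Which rule should apply is a clinical decision outside this point.

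The cost is protocol wording and modest extra data entry and grading for 60 participants. The downside is more low-grade COVID-19 symptoms in the AE listing, which the baseline reference limits but does not remove. With all grades required, 23 of 23 terms would be covered at grade 1 whichever stopping rule is kept.
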